#### **SYNOPSIS**

#### STUDY TITLE

A Phase IB Trial with OTX015/MK-8628, a Small Molecule Inhibitor of the Bromodomain and Extra-Terminal (BET) Proteins, in Patients with Selected Advanced Solid Tumors

#### STUDY OBJECTIVES

#### **Primary**

To determine the Maximal Tolerated Dose (MTD) defined as the recommended phase II dose for two
distinct regimens of OTX015/MK-8628 administered orally to patients with selected advanced solid
tumors

#### **Secondary**

- To assess the safety profile of single-agent OTX015/MK-8628
- To characterize pharmacokinetics parameters of OTX015/MK-8628
- To determine the antitumor activity of OTX015/MK-8628 in selected solid tumors

#### STUDY DESIGN

Open-label, phase I, non-randomized, multicentric study of single-agent OTX015/MK-8628 administered according to two distinct regimens to patients with selected advanced tumors.

The study will be performed in two parts.

#### **Dose Escalation Part**

This step is designed to determine the maximum tolerated dose (MTD) in each of the two regimens, which will be evaluated in parallel. Patients will receive oral OTX015/MK-8628 according to:

Regimen 1: continuous, once daily for 21 consecutive days (21-day cycles).

Or

Regimen 2: once daily on days 1 to 7, repeated every three weeks (21-day cycles; 1 week ON/2 weeks OFF). Patients will be sequentially assigned to Regimen 1 or Regimen 2 according to the next available place and receive OTX015/MK-8628 at escalating doses levels (DL). Cohorts of 3 patients will be treated, and an additional 3 patients will be treated at the first indication of dose-limiting toxicity (DLT). MTD assessment will be based on the tolerability observed during the first 21 days of treatment.

#### **Expansion Part**

The efficacy of OTX015/MK-8628 in each of the five indications (i.e., BRD-NUT midline carcinoma, triple negative breast cancer, non-small cell lung cancer harboring a rearrangement ALK gene/fusion protein or KRAS mutation, castrate-resistant prostate cancer, and pancreatic ductal carcinoma) will be assessed in terms of response (RECIST v1.1 or PCWG2) using a selected regimen.

#### STUDY POPULATION

#### **Inclusion Criteria**

Patients must fulfill all of the following requirements to enter the study:

1. Signed informed consent obtained prior to initiation of any study-specific procedures and treatment;

- 2. Histologically or cytologically confirmed diagnosis of one of the following advanced or metastatic solid tumors for which standard therapy either does not exist or has proven ineffective, intolerable or inacceptable for the patient:
  - NUT midline carcinoma (ectopic expression of NUT protein as determined by IHC and/or detection of BRD-NUT gene translocation as determined by FISH);
  - Triple negative breast cancer defined according to ASCO recommendations (Hammond et al., 2010; Wolff et al., 2007);
  - Non-small cell lung cancer harboring a rearranged ALK gene/fusion protein (FISH or IHC) or KRAS mutation (as defined by any molecular analysis);
  - Castrate-resistant prostate cancer (CRPC);
  - Pancreatic ductal adenocarcinoma;
- 3. At least one measurable lesion as per RECIST version 1.1., except for CRPC patients who may be enrolled with objective evidence of disease as per Prostate Cancer Clinical Trials Working Group (PCWG2) criteria;
- 4. Age  $\geq$  18 years at the time of informed consent;
- 5. Life expectancy  $\geq$  3 months;
- 6. ECOG Performance Status (PS)  $\leq 1$ ;
- 7. Adequate bone marrow reserve, renal and liver function:
  - Absolute neutrophil count  $\geq 1.5 \times 10^9 / L$ ,
  - Platelet count  $\geq 150 \times 10^9 / L$ ,
  - Hemoglobin  $\geq 9$  g/dL (blood transfusion  $\leq 7$  days of screening not permitted),
  - Creatinine clearance ≥ 30 mL/min calculated according to the Cockroft and Gault formula or MDRD formula for patients aged > 65 years,
  - Alanine aminotransferase (ALT), aspartate aminotransferase (AST)  $\leq$ 3 x ULN, if alkaline phosphatase (ALP) > 2.5 X ULN, then liver fraction should be  $\leq$  2.5 X ULN, and total bilirubin  $\leq$  1.25 x ULN (in case of liver involvement, total bilirubin  $\leq$  2 x ULN will be allowed),
  - Serum albumin  $\geq 2.0$  g/dL for NMC,  $\geq 3.0$  g/dL for NSCLC, CRPC, TNBC and pancreatic cancer
  - INR  $\leq$  1.5 or INR  $\leq$  3 for patients treated with antivitamin K;
- 8. An interval of  $\geq 3$  weeks since chemotherapy ( $\geq 6$  weeks for nitrosoureas or mitomycin C), immunotherapy, hormone therapy or any other anticancer therapy or surgical intervention resection, or  $\geq 3$  half-lives for monoclonal antibodies, or  $\geq 5$  half-lives for other non-cytotoxic agents (whichever is longer);
- 9. CRPC patients must maintain ongoing androgen deprivation therapy with a gonadotropin releasing hormone (GnRH) analogue, antagonist or orchiectomy providing serum testosterone is < 50 ng/dL (<1.7 nmol/L);
- 10. Patients receiving bisphosphonate or denosumab therapy must be on stable doses for at least 4 weeks before initiating study treatment.

#### **Exclusion Criteria**

The presence of any of the following criteria excludes a patient from participating in the study:

- 1. Inability to swallow oral medications or presence of a gastrointestinal disorder (e.g. malabsorption) deemed to jeopardize intestinal absorption of OTX015/MK-8628;
- 2. Persistent grade >1 clinically significant toxicities related to prior antineoplastic therapies (except for alopecia); stable sensory neuropathy ≤ grade 2 NCI-CTCAE v. 4.0 is accepted.

- 3. Known primary CNS malignancy or CNS involvement;
- 4. History of prior or concomitant malignancies (other than excised non-melanoma skin cancer or cured *in situ* cervical carcinoma) within 3 years of study entry;
- 5. Other serious illness or medical conditions, such as active infection, unresolved bowel obstruction, or psychiatric disorders;
- 6. Known HIV positivity;
- 7. Participation in another clinical trial or treatment with any investigational drug within 30 days prior to study entry;
- 8. Other concomitant anticancer treatment;
- 9. Concomitant therapy with strong CYP3A4 interfering drugs;
- 10. Current use of anticoagulants (e.g. warfarin, heparin) at therapeutic levels within 7 days prior to the first dose of OTX015/MK-8628. Low-dose (prophylactic) low molecular weight heparin (LMWH) is permitted;
- 11. Pregnant or breast-feeding patients, and men and women with childbearing potential not using effective contraception while on study treatment.

#### STUDY DRUG

### **Study Drug and Formulation**

OTX015/MK-8628 is administered orally. It is provided as size 3 gelatin capsules containing 10 or 20 mg OTX015/MK-8628 (free base) and size 0 gelatin capsules containing 40 mg OTX015/MK-8628 (free base) as a solid molecular dispersion with hypromellose acetate succinate (HPMCAS), mixed with lactose monohydrate, microcrystalline cellulose, croscarmellose sodium, colloidal silicon dioxide, and magnesium stearate excipients. Capsules should be stored at 2°C to 8°C.

#### **Study Drug Administration**

- OTX015/MK-8628 is to be administered *per os* once daily in a fasted state just before breakfast (around 8 a.m. [±2h]), either continuously (Regimen 1) or for 7 consecutive days every 3 weeks (Regimen 2), as a flat dose without adaptation for body weight or surface area.
- A treatment cycle is 3 weeks (21 days).
- Patients participating in pharmacokinetics will be observed for ≥ 8 hours after the first study drug administration to collect PK blood samples and check vital signs, when appropriate.
- Patients should receive the study treatment within 7 days following registration.
- Dosing not performed at the same time (±2h) as on other days will be omitted. Patients are to be instructed that if they vomit or omit their dose in that time frame, it is not to be replaced.

#### **Dose Escalation Scheme**

- Up to four OTX015/MK-8628 dose levels (DLs) are planned for each regimen. Patients will be sequentially assigned to Regimen 1 or Regimen 2, according to the next available place.
- The starting dose will be 80 mg *per os* given once daily for Regimen 1, and 100 mg given once daily for 7 days every 3 weeks for Regimen 2.
- DLT assessment in each regimen will be independent and based on tolerability observed during the first 21 days of study treatment.
- The first patient enrolled in a higher DL cohort will not start the study treatment until the last treated patient in the DL immediately below has completed 3 weeks of study treatment.
- If 1/3 patients of a cohort has DLT during cycle 1 (i.e. the first 21 days following study treatment

initiation), up to 3 additional patients will be entered at this DL. If no more than 1/6 evaluable patients has DLT, dose escalation will proceed to the DL immediately above. If more than 1/6 patients (or more than 1/3) has DLT, the DL will be considered to exceed the MTD (see table below).

• Patients not evaluable for DLT (i.e. receiving less than 85% of the intended cumulative dose of the first 21-day cycle period for any reason other than toxicity; <18 days of treatment for Regimen 1, or <6 days of treatment for Regimen 2) and who do not experience DLT will be replaced.

_	OTX015 Do	se (mg/day)		
Dose	Regimen 1	Regimen 2	Outcome (#DLT/#Patients)* / Actions to be taken	
Level	(continuous)	(D1-7, q3w)		
DL 1	80	100	At each DL for each regimen:	
DL 1	00	100	- If 0 of 3 patients has DLT, escalate dose in next cohort of 3 patients	
DL 2	100	120	- If 1 of 3 patients has DLT, treat next 3 patients at the same dose level (6 patients total)	
DL 3	120	160	- If ≥ 2 of 3 patients has DLT, halt dose escalation (MTD exceeded)	
			- If 1 of 6 patients has DLT, escalate dose for next cohort of 3 patients	
DL 4	160	200	- If ≥ 2 of 6 patients has DLT, halt dose escalation (MTD exceeded)	

\* Evaluated during the first 21 days of treatment

## **DLT Definition**

A DLT is defined as any of the following toxicities occurring during the first 21 days of treatment and considered by the investigator to be related to OTX015/MK-8628.

## Hematologic toxicity

- Any grade 4 hematologic toxicity or febrile neutropenia
- Grade 3 neutropenia with infection
- Grade 3 thrombocytopenia with bleeding or lasting > 7 days

## Non-hematologic toxicity

- Any grade 3 or 4 non-hematologic toxicity (regardless of duration) unless it was not optimally managed with supportive care (e.g. grade 3 vomiting not adequately treated according to antiemetic standard of care).
- Any grade 3 or 4 laboratory abnormality, with or without symptoms, lasting > 48 hours.
- Any intolerable grade 2 non-hematologic toxicity resulting in study drug discontinuation or delay > 7 days with or without dose reduction.
- Any of the following liver test abnormalities\*\* (see Appendix 5)
  - ALT or AST  $> 8 \times ULN$
  - ALT or AST > 5 x ULN for > 2 weeks
  - ALT or AST > 3 x ULN AND (total bilirubin > 2 x ULN OR INR > 1.5)
  - ALT or AST > 3 x ULN with the appearance of fatigue, nausea, vomiting, right upper quadrant pain or tenderness, fever, rash and/or eosinophilia (> 5%)

#### Other

- Treatment delay > 2 weeks or dose reduction requirement for initiating cycle 2.
- \*\*Note: All patients with these liver test abnormalities should be monitored weekly until all abnormalities return to normal or to the baseline state. For patients with isolated total bilirubin increases >2 x ULN or 2 x baseline (if elevated at baseline), monitoring should be every 2 weeks until bilirubin returns to normal or to the baseline state. Drug induced liver injury (DILI) may develop or progress even after the causative drug

has been stopped. Results should be recorded on the CRF and in the database. See guidelines on the handling of these events (potential Hy's law cases)

## MTD (recommended phase II dose) Definition

The MTD is defined as the dose immediately preceding the DL at which DLTs are observed in  $\geq 2$  out of 3 to 6 patients; i.e., the DL at which 0 of 3 patients or  $\leq 1$  of 6 patients experience DLT. The MTD will be determined in each of the two regimens evaluated.

#### **Expansion Part**

Once the MTD is established for each regimen with at least 3 patients having received at least 2 evaluable cycles of study drug, the study will be extended with the inclusion of 10 evaluable patients per indication at the MTD. The regimen used in each expansion cohort (i.e., each indication) will be decided by the SMC.

## **Prophylactic and Concomitant Medications**

- No premedication is planned.
- During the study, patients must not receive other investigational drugs, agents or devices, or any other therapy for cancer treatment.
- Drugs given with prophylactic intent are not permitted during cycle 1.
- Patients requiring biphosphonates or denosumab therapy must have been on stable doses for at least 4 weeks prior to study entry. Bisphosphonates or denosumab are permitted from cycle 3.
- Use of anticoagulants (e.g. warfarin, heparin) at curative therapeutic levels within 7 days prior to the study treatment start is not allowed. Preventive low-dose LMWH or antivitamin K (INR < 3) are permitted. INR must be monitored in accordance with local institutional practices.
- For prostate cancer patients, concomitant androgen deprivation therapy with GnRH analogue or antagonist is mandatory unless the patient had previous bilateral orchiectomy as part of his hormone therapy.
- All other medication necessary for the well-being of the patient and which is not expected to interfere with evaluation of the study drug may be given at the investigator's discretion.
- Use of strong CYP3A4 interfering drugs/substances is not permitted. The concomitant use of other CYP3A4 interfering drugs or any CYP2A6 interfering drug is allowed provided a careful follow-up of laboratory results that may be influenced by the concomitant agent is performed (e.g. INR if the concomitant agent is an anticoagulant, blood cell counts if the concomitant drug is hematotoxic must be followed up more frequently than required by the protocol)(Appendix 3).

#### Treatment Adaptation

OTX015/MK-8628 will be interrupted until recovery to  $\leq$  grade 1 or baseline value and the dose reduced or the schedule modified in the event of:

#### Hematologic toxicity

- Any grade 4 hematologic toxicity or febrile neutropenia
- Grade 3 neutropenia with infection
- Grade 3 thrombocytopenia with bleeding or lasting > 7 days

## Non-hematologic toxicity

- Any grade 3 or 4 non-hematologic toxicity (regardless of duration) unless it was not optimally managed with supportive care (e.g. grade 3 vomiting not adequately treated according to antiemetic standard of care).
- Any grade 3 or 4 laboratory abnormality, with or without symptoms, lasting > 48 hours.
- Any intolerable grade 2 non-hematologic toxicity resulting in study drug discontinuation or delay > 7 days with or without dose reduction.

No more than two dose reductions (or schedule modifications) should be implemented, unless the investigator thinks it in the patient's best interests to pursue study treatment with a further dose reduction (an additional dose level), with the Sponsor's agreement.

Dose / Schedule Modifications: Regimen 1					
Initial OTX015 Dose	1st Modification	2 nd Modification			
80 mg QD continuously	80 mg QD, 2 weeks ON/ 1 week OFF, q3w	60 mg QD, 2 weeks ON/1 week OFF, q3w			
100 mg QD continuously	100 mg QD, 2 weeks ON/1 week OFF, q3w	80 mg QD, 2 weeks ON/1 week OFF, q3w			
120 mg QD continuously	120 mg QD, 2 weeks ON/1 week OFF, q3w	100 mg QD, 2 weeks ON/1 week OFF, q3w			
160 mg QD continuously	160 mg QD, 2 weeks ON/1 week OFF, q3w	120 mg QD, 2 weeks ON/1 week OFF, q3w			

Dose / Schedule Modifications: Regimen 2											
Initial OTX015 Dose	1st Modification	2 nd Modification									
100 mg QD, Days 1-7, q3w	80 QD, Days 1-7, q3w	60 QD, Days 1-7, q3w									
120 mg QD, Days 1-7, q3w	100 mg QD, Days 1-7, q3w	80 QD, Days 1-7, q3w									
160 mg QD, Days 1-7, q3w	120 mg QD, Days 1-7, q3w	100 mg QD, Days 1-7, q3w									
200 mg QD, Days 1-7, q3w	160 QD, Days 1-7 q3w	120 mg QD, Days 1-7, q3w									

Dosing interruption for > 2 weeks due to toxicity or liver toxicity (see treatment duration for details) will lead to definitive study treatment discontinuation unless the investigator thinks it is in the patient's best interests to pursue study treatment, with the Sponsor's agreement.

#### **Safety Monitoring Committee**

An SMC is responsible for making final decisions on stopping dose escalation, further dose escalation, determining the RD and starting cohort expansion enrollment. According to the nature, suspected relationship to study drug, or other clinical considerations, the SMC will make *ad-hoc* decisions, such as replacing non-evaluable patients, adding more patients at the same DL, adding intermediate DLs, exploring additional doses and/or regimens (e.g., if the MTD is not reached at the highest dose), not considering a given DLT as clinically relevant for the determination of the RD, progressing with the dose expansion part, and the regimen to be followed in each indication in the expansion part of the study. Serial assessments of PK results may be taken into account for the determination of the MTD.

The SMC will be composed of the principal investigators of each participating center, the pharmacokinetics specialist, the medical and safety representatives of the Sponsor, and an independent medical expert in oncology drug development. All decisions made by the SMC and their rationale will be recorded in meeting minutes.

#### **Duration of Treatment (per patient)**

Treatment will be continued until:

- Disease progression
- Unacceptable toxicity
- Patient withdrawal of consent
- Patient non-compliance
- Treatment interruption > 2 weeks for any reason (except in the event of perceived benefit, with Sponsor agreement)

- Recurrence of DLT despite dose reduction (except in the event of perceived benefit, with Sponsor agreement)
- Any of the following liver test abnormalities\*\* (see Appendix 5)
  - ALT or AST  $> 8 \times ULN$
  - ALT or AST > 5 x ULN for > 2 weeks
  - ALT or AST > 3 x ULN AND (total bilirubin > 2 x ULN OR INR > 1.5)
  - ALT or AST > 3 x ULN with the appearance of fatigue, nausea, vomiting, right upper quadrant pain or tenderness, fever, rash and/or eosinophilia (> 5%)

#### **Duration of Observation**

Patients are to be followed up for safety for at least 30 days following the last OTX015/MK-8628 dosing and until recovery or stabilization of all related toxicities. Tumor measurements are to be made every 6 weeks and bone scans will be performed every 12 weeks until progressive disease is observed.

## **Treatment Compliance**

Patients will record daily in a diary, the number of OTX015/MK-8628 capsules swallowed, time of intake, as well as any eventual reactions, including vomiting, and their time of occurrence. At each study visit the hospital pharmacist of the study center will provide the patient with the necessary number of OTX015/MK-8628 capsules until the next visit and retrieve any unused capsules/vials that will be kept until study end for accountability.

#### **ASSESSMENTS**

## Activity

Disease assessments (RECIST version 1.1 or PCWG2) will be made at baseline (within 4 weeks prior to treatment start). Tumor measurements (using the same method as at baseline) will be made every 2 cycles (q6w) and bone scans every 4 cycles (q12w) until progression. Objective responses must be confirmed at least 4 weeks after first documentation. PCWG2 criteria will be used for CRPC patients.

#### **Safety**

Adverse events will be evaluated throughout the study and graded according to the NCI-CTCAE v4.03. A physical examination will be performed and vital signs evaluated before each cycle. Hematology laboratory values will be assessed twice weekly for the first 2 cycles and weekly thereafter, and biochemistry laboratory values will be assessed weekly for the first 2 cycles and every cycle thereafter.

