#### STUDY SCHEDULE

Parameter		Day 1 visit		Weekly	Day 1	Treatment
	visit	every	week	cycles	visit of	discontinuation
	(≤2 weeks	cycle	cycles 1+ 2	1+2	C3, C5,	visit (35±5 days)
	before		then		C7 etc.	after last
	treatment)		weekly			treatment intake
Informed consent	X					
Eligibility criteria	X					
Demographics, medical history	X					
Diagnosis, prior treatment for malignancy	X					
Physical examination, PS, vital signs 	$X^1$	X				X
Pregnancy test if child-bearing potential	X					
(urine test)						
Baseline symptoms and complaints	X					
Concomitant medication	X	X				X
Complete blood count (CBC) 	X	X	X			X
INR and Factor VII	X	X		X		X
Serum chemistries 	X	$X^3$		$X^3$		X
Drug dispensation						
Regimen 1		QD				
		continuous				
Regimen 2		Days 1-7				
		q3w				
Adverse events		X				X
CT, MRI, chest X-ray (PA and lateral),	$X^4$			<del>-</del>	$X^4$	X
bone scan						
Tumor markers 	X	X				X
PK blood sampling		$X^6$				
Other investigations as indicated	X	X		X		X

- 1) Vital signs include temperature, blood pressure, and pulse; Body weight at each visit and height at baseline only;
- 2) Hemoglobin, RBC counts, WBC and differential, platelet counts;
- 3) Minimum: Na, K, Ca, Mg, P, Cl, HCO3, creatinine, total protein, albumin, glucose, alkaline phosphatase, total bilirubin, AST, ALT, LDH; from cycle 3 on, in the absence of  $\geq$  grade 2 abnormalities, these tests will be performed every cycle, otherwise they are to be done weekly until resolution to baseline levels or < grade 2. All patients with specific liver test abnormalities (see DLT definition) should be monitored weekly until all abnormalities return to normal or to the baseline state. For patients with isolated total bilirubin increases >2 x ULN or 2 x baseline (if elevated at baseline), monitoring should be every 2 weeks until bilirubin returns to normal or to the baseline state;
- 4) Radiologic exams (CT, MRI, chest X-ray) performed as part of the patient's standard follow-up within 4 weeks prior to the first treatment cycle, are acceptable. Radiologic assessment will be performed every 2 cycles (6 weeks) as per RECIST 1.1 or PCWG2 until progression; Bone scans are mandatory in CRPC patients and will be performed every 4 cycles (12 weeks) until progression;
- 5) As appropriate for tumor type;

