# **Pharmacokinetic Findings**

PK showed dose-proportional increases in exposure ( $C_{max}$  and AUC) from 10 mg to 120 mg QD, (see Figure 2).  $T_{max}$  occurred between 1 and 4 hours (for the oral formulation used in this study  $T_{max}$  is expected between 1 to 3 hours, but limited sampling points precluded more accurate assessment of T and  $C_{max}$ ). Mean clearance was 9.9 (range, 6-12) L/h, mean volume of distribution was 68 L, and mean terminal half-life was 4.7 (range, 3.2-5.7) hours. Preliminary population PK analysis suggests that interpatient variability may be explained by lean body mass and/or body weight. These parameters appear to play a role in clearance variation, as patients with higher lean body mass display increased clearance and volume of distribution.

Trough (pre-dose) Dose N pts  $C_{max}$ AUC0-24h Cy1D1 Cy1D8 Cyl D1 (nM) (nM)  $(\mu g \cdot h/L)$ DL1 8 267 46 962 10 mg QD (121 - 424)(18 - 81)(648 - 1,349)103 2,592 DL 2 6 560 (357 - 844)(84 - 127)(1,809 - 4,223)20 mg QD DL3 8 1,274 230 4,722 40 mg QD (663 - 3,029)(53 - 897)(3,951 - 5,292)7 424 10,420 DL4 2,539 (1,085 - 4,593)(152 - 1331)(7,229 - 15,760)80 mg QD **DL4 BID** 13 1,128 638 10,540 (269 - 924)40 mg x 2 (699 - 1,810)(5,898-19,720)DL5 13 2,383 764 14,815\* (194 - 2,016)120 mg QD (1,412 - 4,055)(9,522 - 26,953)

Table 8: Mean (range) PK parameters (N=47)

The BID schedule was explored to maintain or increase trough concentrations, while not increasing  $C_{max}$ . This goal was achieved, as trough concentrations were significantly higher with the BID schedule, compared to the QD schedule, with the same daily dose, while similar exposures were obtained. Likewise, trough concentrations at DL5 (120 mg) QD achieved similar or higher trough concentration than 40 mg BID. Since both dose/schedule exceed the MTD for OHM patients, it is tempting to assume that thrombocytopenia is related to continuous high trough concentration.

[figure not shown]

Figure 2: Individual AUC0-24h versus Dose Level

\*AUC calculated on 12 patients only

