# Regimen 2: Days 1-7, every 21 days

A starting dose of 100 mg OTX015 administered orally once daily for 7 consecutive days, repeated every 3 weeks will be explored in an attempt to determine if discontinuous drug administration can reduce:

- 1) The incidence and severity of thrombocytopenia which appears to be the most common toxicity of OTX015 in patients with hematologic malignancies, emerging at ≥ 80 mg daily continuous dose after nearly 2 weeks of treatment exposure (grade 3-4 thrombocytopenia occurred in 50% of patients with 28% having a grade 4), with an incidence/severity appearing to increase with dose suggesting a possible schedule-dependency.
- 2) Given that in the ongoing phase I study in patients with advanced hematologic malignancies, severe thrombocytopenia tends to occur after approximately 2 weeks of continuous treatment, and that furthermore a recovery interval of approximately 10 days is required for severe thrombocytopenia to return to lower grades, a discontinuous regimen may be required to allow re-treatment every 3 weeks. This is important to take into account for future combination clinical studies.

These two regimens (with or without recovery period) will be tested in parallel, i.e., Regimen 1 (daily continuous dosing) and Regimen 2 (7 days every 21 days). This will allow selection of the optimal regimen for further studies in terms of balance between tolerability, pharmacokinetics and antitumor activity.

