# 5.2.2 Schedule

OTX015/MK-8628 is to be administered *per os* once daily in a fasted state with a little water just before breakfast (around 8 a.m. [±2h]). Flat doses will be used with no adjustment for BSA or weight.

Two regimens will be evaluated; OTX015/MK-8628 will be administered either continuously (Regimen 1) or for 1 week ON/2 weeks OFF (Regimen 2). Capsules must not be opened or chewed.

A treatment cycle is 21 days (3 weeks). The subsequent cycle will begin on day 22 or after recovery from any AEs associated with the previous cycle.

Patients should receive study treatment within 7 days following registration.

Dosing not performed at the same time  $(\pm 2h)$  as on other days will be omitted. Patients are to be instructed that if they vomit or omit their dose in that time frame, it is not to be replaced.

Details of the exact dose and time of administration will be documented in a patient diary and reported in the electronic case report form (eCRF).

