# 7.2 Evaluations During Study Treatment

#### Visit: Day 1 of each cycle

For cycle 1, patients participating in pharmacokinetics will be observed for  $\geq 8$  hours after the first study drug administration to collect PK blood samples and check vital signs, when appropriate.

- Physical examination, PS, vital signs, body weight
- CBC
- INR, Factor VII
- Serum chemistries: all patients with specific liver test abnormalities (see Section 5.2.4) should be monitored weekly until all abnormalities return to normal or to the baseline state. For patients with isolated total bilirubin increases >2 x ULN or 2 x baseline (if elevated at baseline), monitoring should be every 2 weeks until bilirubin returns to normal or to the baseline state. DILI may develop or progress even after the causative drug has been stopped.
- Concomitant medications
- Adverse events
- Tumor markers, as appropriate for tumor type; as far as possible, measures must be made in the same laboratory
- Dispensing of study drug (adequate quantity until day 1 visit of next cycle)
- Day 1 of cycle 1 only: PK blood sampling in patients included in the dose escalation part of the study and selected patients from the expansion cohort (see Section 10 for full PK details): T0 (just before OTX015/MK-8628 intake), T15min (±5 min) post-dose, T1h (±15 min) post-dose, T2h (±15min) post-dose, T3h (±15min) post-dose, and T7h (±15min) post-dose
- Day 1 of every 2nd cycle (C3, C5, C7, etc.; i.e., every 6 weeks): Tumor imaging (CT, MRI, and/or chest X-ray, as indicated) and response assessment
- Day 1 every 4th cycle (C5, C9, C13 etc.; i.e., every 3 months): Bone scan for CRPC patients

Twice a week for cycles 1 and 2 then weekly thereafter

CBC

Weekly for cycles 1 and 2

- Serum chemistries; from cycle 3 on, in the absence of  $\geq$  grade 2 abnormalities these tests will be performed every cycle; otherwise they are to be done weekly until resolution to baseline levels or  $\leq$  grade 2.
- INR, Factor VII

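### From cycle 3, chemistry and INR/Factor VII abnormality rates are not comparable between regimens, because the routine Regimen 2 draw follows 14 drug-free days

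*Protocol*

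**What the plan says.** Regimen 1 is dosed every day of a 21-day cycle. Regimen 2 is dosed on days 1 to 7 and then stopped for two weeks (Protocol, Synopsis and Section 3.1). On when the next cycle starts, Section 5.2.2 says: "The subsequent cycle will begin on day 22 or after recovery from any AEs associated with the previous cycle".

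For both regimens the Synopsis says that "biochemistry laboratory values will be assessed weekly for the first 2 cycles and every cycle thereafter". Section 7.2 and the study schedule place chemistry, INR and Factor VII on day 1 of every cycle, with extra weekly draws in cycles 1 and 2 only. From cycle 3 the chemistry frequency depends on grade. If there is no grade 2 or higher abnormality, "these tests will be performed every cycle, otherwise they are to be done weekly until resolution to baseline levels" or a lower grade (study schedule, footnote 3). Specified liver-test abnormalities are followed weekly. INR and Factor VII have no grade rule of their own. Blood counts are twice weekly in cycles 1-2 and weekly after that.

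Laboratory abnormalities are a secondary safety endpoint with no limit on cycles (Protocol 11.2, SAP 2.4). SAP 2.6 breaks results down by dose level and regimen and does not mention cycle. On the purpose of running the two regimens in parallel, Section 1.4.2 says: "This will allow selection of the optimal regimen for further studies in terms of balance between tolerability, pharmacokinetics and antitumor activity". Section 8.1 also promises a look for cumulative toxicity over repeated cycles.

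**The concern.** Day 1 means different things in the two regimens. In Regimen 1 it follows 21 consecutive days of dosing; in Regimen 2 it follows two weeks without drug. In cycles 1-2 this does little harm, because a weekly draw also falls at the end of the Regimen 2 dosing week. From cycle 3 that draw goes, and a by-regimen table then mixes on-treatment values with off-period values.

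The tests concerned have already shown signals with this drug. Section 1.3.2.3 names the digestive system, particularly the liver, as the main target organ in animals. In the hematologic malignancy study, adding Tables 6 and 7 (30 + 32 = 62 patients) gives related hyperglycemia in 11 patients, Factor VII decrease in 8 and direct bilirubin increase in 4. Later cycles are not negligible either: in that study 17 of 52 patients with enough follow-up (33%) received more than 3 cycles.

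At stake is the reading of a secondary safety endpoint, between regimens and also across cycles within Regimen 2. An apparent fall in abnormalities from cycle 3 could come from the change in sampling alone.

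**Working it through.** **1. The plan's own figure.** Drug-free days in a Regimen 2 cycle: 21 − 7 = 14 (days 8 to 21). This matches the two weeks off that the protocol states.

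**2. Time from last dose to the day 1 draw.** From the day 7 dose to day 22 is 15 × 24 = 360 h. Section 1.3.3.2 reports that "mean terminal half-life was 4.7 (range, 3.2-5.7) hours".
- At 4.7 h: 360 / 4.7 = 76.6 half-lives.
- At 5.7 h and 3.2 h: 63.2 and 112.5.
- At 16.3 h, the top of the healthy-volunteer range with another formulation: 22.1.

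Drug is cleared by the draw. This says nothing about how fast a laboratory value recovers. A delayed cycle start lengthens the interval further.

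**3. Scheduled draws during dosing or within 24 h of a dose, not counting the draw that opens the cycle.** This takes weekly draws as counted from day 1.
- Regimen 2, cycles 1-2: one per cycle (day 8).
- Regimen 2, cycle 3 onward: none, unless the grade rule or liver follow-up is already active.
- Unmodified Regimen 1: every draw after the first dose.

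**4. Size, as an illustration.** The documents give no duration for chemistry or INR/Factor VII abnormalities, so the duration D is assumed. Onset is taken as uniform over the dosing days: days 1 to 22 in Regimen 1, days 1 to 8 in Regimen 2. An episode counts as detected if it is present at a scheduled draw. Then, with each probability kept between 0 and 1:
- Next day 1 only (day 22), Regimen 1: P = D / 21.
- Next day 1 only, Regimen 2: P = (D − 14) / 7.
- Weekly (days 8, 15, 22), both regimens: P = D / 7.

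| D (days) | Day 1 only, Regimen 1 | Day 1 only, Regimen 2 | Weekly, both |
|---|---|---|---|
| 3 | 0.14 | 0.00 | 0.43 |
| 7 | 0.33 | 0.00 | 1.00 |
| 10 | 0.48 | 0.00 | 1.00 |
| 14 | 0.67 | 0.00 | 1.00 |
| 18 | 0.86 | 0.57 | 1.00 |
| 21 | 1.00 | 1.00 | 1.00 |

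A simulation under the same assumptions gave the same values. The regimens agree under weekly draws, and again once episodes last 21 days. They differ in between.

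**5. Across cycles.** For a 7-day episode, detection falls at cycle 3 from 1.00 to 0.33 in Regimen 1 and from 1.00 to 0.00 in Regimen 2. A by-cycle trend is therefore affected by sampling in both regimens, and more so in Regimen 2.

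**The case against.** The strongest reply is that the decisions in this trial do not use cycle 3 chemistry. The primary endpoint and the MTD rest on cycle 1, and expansion requires three patients with two evaluable cycles. All of that lies inside the weekly window. Thrombocytopenia, the toxicity that motivates Regimen 2, is followed by blood counts at equal frequency in both regimens, and clinical adverse events are collected throughout. This stands, and it limits the point to one group of laboratory tests from cycle 3.

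Second, the SAP plans no formal contrast. Allocation is not randomized, doses differ between regimens, and results are only described. The SAP also speaks of the once-daily regimens in the past tense and describes a twice-daily part 2. This stands as to weight. But a by-regimen table invites comparison even without a test, and Section 1.4.2 gives that comparison as a purpose.

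Third, the grade rule can be triggered by an unscheduled test, and an unresolved cycle 2 abnormality carries weekly chemistry forward. This stands in part. A new abnormality arising after cycle 2 must still be found on day 1, through symptoms or by an unscheduled test. Weekly follow-up of the specified liver abnormalities may bring in an INR, but only once such an abnormality is known.

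Fourth, the percentages follow from assumed onset and duration. The only recovery figure in the documents, about 10 days, is for platelets. This stands: the table shows direction and plausible size and is not an estimate.

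A reader might also infer that the Regimen 2 day 1 draw shows only recovery, or that a liver signal recurring every cycle would go unseen. The documents support neither. Section 7.2 warns that liver injury may appear or worsen after the drug is stopped, so delayed and persistent abnormalities are still caught. A signal present in every cycle would already show under the weekly draws of cycles 1-2.

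**Conclusion.** The point holds within limits. From cycle 3, a Regimen 2 patient with no known grade 2 or higher abnormality has routine chemistry only after 14 drug-free days, and INR/Factor VII is drawn only on day 1 regardless of grade. Unmodified Regimen 1 is drawn under continuous dosing. Rates of these abnormalities from cycle 3 are therefore not comparable between regimens, nor between early and late cycles within Regimen 2. Under the assumed durations, detection is 0% against 33% for 7-day episodes and 0% against about 48% for 10-day episodes. The gap closes at 21 days.

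The tempting stronger conclusion is that Regimen 2 looks safer overall by construction. The documents do not support it: the cycle 1 DLT endpoint, the MTD, blood counts and clinical adverse events are unaffected. Nor is the contrast uniform. Regimen 1 patients moved to two weeks on and one week off are themselves drawn after 7 drug-free days, and under the same model Regimen 1 misses more than half of 10-day episodes.

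**What to change.** In SAP 2.6, base the by-regimen presentation of chemistry and INR/Factor VII abnormalities on cycles 1-2, where both regimens have weekly draws. State that the cycle 3 day 1 sample closes cycle 2; the equality in the working depends on it. Tabulate later draws separately. Label them as values after the off period for Regimen 2, and likewise for Regimen 1 patients moved to two weeks on and one week off. Apply the same split to any cumulative-toxicity summary under Protocol 8.1.

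The cost is a few sentences of SAP text, fewer cycles in the main table and one extra table. No new data are needed.

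Optionally, and only if Regimen 2 dosing is still ongoing, consider running chemistry and INR/Factor VII on the weekly blood-count draw that falls at the end of the dosing week. That adds a small laboratory cost and a schedule amendment, but no visit.

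Separately, the study schedule ends weekly chemistry at below grade 2, while Section 7.2 ends it at grade 2 or below. The two passages must be reconciled, since they decide which later-cycle chemistry values exist.
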